*Established expertise in neuroimaging of TBI.* Our group has also been very active in the longitudinal study of TBI patients, utilizing multimodal neuroimaging and neuropsychological testing to assess biomarkers of injury and recovery. In adult and pediatric mTBI populations we have documented deficits in attention, post-traumatic symptoms, diffusion tensor abnormalities, neurometabolites, and fMRI differences, both in the semi-acute phase and in the chronic phase (4 months post-injury). We have used fMRI to examine attentional dysfunction in patients with TBI, observing decreased activation in both sub-cortical and cortical networks. The PI of this project has been providing clinical care for brain injured patients on an inpatient neurosurgical service and in an outpatient neuropsychiatry clinic for the past five years, and has ample experience with retention, characterization, and treatment of this clinical population. MRI sequences for characterization of TBI may be obtained as part of baseline and post-stimulation assessment in a subgroup of mmTBI subjects. The advantage of obtaining neuroimaging in this study is three-fold: 1) structural abnormalities may affect current flow and alter the effectiveness of TDCS; 2) TDCS has been shown by our group to increase glutamate under the anodal electrode, and use of MRS to characterize neurometabolite flux before and after stimulation could add important evidence to this theory; 3) mmTBI may cause functional brain activation abnormalities independent of structural lesions that can be correlated and localized with EEG.

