### **Inclusion Criteria**

Patients seen the emergency department (ED) will be enrolled in this study if they 1) are aged 18-55, 2) have suffered a TBI with documented evidence of loss of consciousness (LOC) which was less than 24 hours, 3) were injured between 3 months and 15 years ago, 4) received a Glasgow coma scale (GCS) score of between 9 and 15 upon ED admission, 5) experienced less than 1 week of post-traumatic amnesia (PTA), and 6) have post-traumatic cognitive symptoms as evidenced by endorsing at least 1 out of 4 cognitive symptoms on the Neurobehavioral Symptom Inventory (NSI), a measure of post-traumatic symptoms from the NIH Common Data Elements, and 7) have been on stable doses of any psychotropic medications for the past 2 months.. Healthy controls will be between the ages of 18-55.

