Randomization will occur at time of consenting. The study coordinator who consented the patient will use a coin-tossing procedure to determine whether the subject is assigned to the active group (group 1) or control group (group 2). Modifications will be made as necessary toward the end of enrollment to ensure equal group size and balanced distribution of demographic variables such as age and gender. The study coordinator will not be blinded to group assignment, and with the assistance of the Clinical Core, will program the TDCS devices to deliver active or sham stimulation depending on which group the subject has been assigned. However, the coordinator will not be involved in performing any stimulation procedures. The study technician and principle investigator, who will be responsible for administering the stimulation, will not be aware of which group receives active versus control, and will thus be blinded, as the TDCS device will only display the group number (1 or 2).

Once group membership is determined, individual participants may undergo demographic data collection, neuropsychological assessments and tDCS treatment sessions. They may also undergo EEG and/or MRI. Direct identifiers of participants will be maintained on a separate database that will be stored behind locked doors, in a locked filing cabinet in a secure area of the Clinical Core.

**Demographic Data:** As part of the initial assessment, basic demographic data regarding the subject may be noted down, including age, gender, socioeconomic status, educational attainment, handedness, use of common stimulants such as caffeine, and brain injury severity. They may also be asked if they are willing to allow their medical record to be accessed, for the purposes of confirming details about any TBI as well as obtaining results of neuroimaging studies done at the time of injury or afterward. This will include medical, surgical, neurological and psychiatric history, results of lab tests, brain scans, electroencephalography tests, medication lists, information from doctor's visits and hospital visits.

**Neuropsychological testing procedures:** All neuropsychological testing will be administered in the Center for Brain Recovery and Repair Core by trained study personnel under direct supervision of core directors, clinical neuropsychologists Drs. [name], [name], or the PI. The primary dependent outcome variables to be studied are the three composite scores generated by

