Statistical analyses will utilize the CTSC Biostatistics core. Power analyses and statistical analysis strategy were determined with our statistician [name], who will continue to provide recommendations and support throughout the project. Sufficient group sizes were determined on the basis of data derived from preliminary studies. Clark and colleagues found an effect size of Cohen's  $d = 1.2$  for tDCS to induce improvements in cognition. For our power calculations we will assume a more conservative effect size of  $d = 0.7$  which is consistent with a recent meta-analysis of tDCS effect sizes. With 40 tDCS treatment patients compared to 40 sham patients and an effect size of 0.7, we have 80% power to detect effects of active versus sham treatment in a two-sample t-test. Power in the linear mixed model analysis should be superior that that of the t-test. For Aim 1.1, the central analyses evaluate group (active vs. sham) differences in the EEG data and on the three Examiner composite variables across the three initial time points (before, immediately after, and 1 month after tDCS stimulation protocol). To test this hypothesis, three separate linear mixed models analyses will be performed using the three Examiner composite scores (Fluency, Cognitive Control, Working Memory) as dependent variables. In each analysis, we will incorporate three covariates that may predict variation in learning (severity: mild vs. moderate, premorbid intelligence: WTAR score, and symptom burden: NSI). This will allow us to determine predictors of treatment response (Specific Aim 1.3). Sex, ethnicity, and age will also be entered into the statistical model. The effects of these covariates will be estimated by constructing appropriate contrasts in model effects. A similar set of analyses will evaluate group differences on the variables assessed in our long-term oral/phone follow-up (five data points: (1) before tDCS, (2) immediately after tDCS, (3) 1 month post-tDCS, (4) 6 months, and (5) 1 year) for Aim 1.2. For these analyses dependent variables will be the total cognitive items score of the NSI and the PROMIS-29 profile total score). Significant effects will be followed up with more fine-grained analysis of the components of composite scores. The use of linear mixed-models minimizes the adverse impact of a missing data point, which may well occur in a longitudinal clinical study such as this. Expected attrition will be taken into account with an intention-to-treat analysis. Missing data patterns will be analyzed to assess the extent to which they are informative (in contrast to missing at random), and analyses adjusted accordingly. All EEG data will undergo standard preprocessing (e.g. motion correction, spatial normalization) and quality control prior to statistical modeling. Depending on the specific question of the study, data may be analyzed using the general linear model, independent components analysis, machine learning techniques, or a variety of other standard approaches for neuroimaging data.

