We will also provide all participants and their families with a referral list of community support, treatment, and educational resources about TBI. This information will also be explained during the consent process. In addition, if a participant's status with respect to any of the study criteria change during the experiment (i.e., initiation of substance abuse), the participant's participation in the study may be terminated without their consent. Our consent form will include a statement regarding anticipated circumstances under which the subject's participation may be terminated by the investigator without regard to the subject's consent and a statement indicating that significant new findings developed during the course of the research which may relate to the subject's willingness to continue participation will be provided.

Statistical analyses will utilize the CTSC Biostatistics core. Power analyses and statistical analysis strategy were determined with our statistician [name], who will continue to provide recommendations and support throughout the project. For Aim 1.1, the central analyses evaluate group (active vs. sham) differences on the three Examiner composite variables across the three initial time points (before, immediately after, and 1 month after tDCS stimulation protocol). To test this hypothesis, three separate linear mixed models analyses will be performed using the three Examiner composite scores (Fluency, Cognitive Control, Working Memory) as dependent variables. In each analysis, we will incorporate three covariates that may predict variation in learning (severity: mild vs. moderate, premorbid intelligence: WTAR score, and symptom burden: NSI). This will allow us to determine predictors of treatment response (Specific Aim 1.3). Sex, ethnicity, and age will also be entered into the statistical model. The effects of these covariates will be estimated by constructing appropriate contrasts in model effects. A similar set of analyses will evaluate group differences on the variables assessed in our long-term oral/phone follow-up (five data points: (1) before tDCS, (2)

**PROTOCOL TITLE:** Transcranial direct current stimulation for treatment of deficits after traumatic brain injury.

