## **15. Data and Specimen Banking (see section on Data Management)**

## **16. Risks to Subjects**

Participation in this study for both healthy controls and mmTBI subjects may involve minor risks and/or discomforts associated with possible breach of confidentiality risk, neuropsychological testing, MRI, EEG, and tDCS.

**MRI:** Radio and magnetic waves associated with MRI scans are not associated with any known adverse effects. MRI is non-invasive and considered minimal risk by the FDA and OHRP. However, the scanner is a large magnet, so it could move objects containing ferrous metal in the room during the scan. All control and mmTBI participants are screened using the MRI safety screening form prior to being scanned. Participants with any MRI scanning contraindications will be excluded from study participation. Participants may be bothered by feelings of

**PROTOCOL TITLE:** Transcranial direct current stimulation for treatment of deficits after traumatic brain injury.

claustrophobia (uncommon). The MRI also makes loud ‘drum’ beating noises during the study. Headphones are provided for protection. Rarely, large or recent tattoos can heat up during an MRI scan and cause skin irritation like a sunburn (uncommon). No long-term harmful effects from MRI are known. However, since the effect of MRI on early development of the fetus is unknown, participants who are pregnant will not be allowed to go in the MRI. Females 18 years of age or older who suspect they may be pregnant will be asked to take a urine pregnancy test before being allowed to participate in the study. The test results will only be shared with participant.

**Neuropsychological tests.** The neuropsychological tasks involved in the protocol entail no foreseeable risk, besides perhaps fatigue or mild to moderate demands on attention and cognition. These are typically very marginally significant risks, mitigated by the fact that if a patient fatigues during testing they are given a rest break or are rescheduled. There is also mild psychological risk inherent in testing participants for cognitive abilities.

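### Ending study participation when any study criterion changes can make 6- and 12-month retention depend on outcome and weakens the intention-to-treat plan; separately, the MRI rule excludes randomised participants needlessly

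*Combined protocol and SAP*

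**What the plan says.** **Termination rule.** Section 14 (Data Management/Confidentiality) sets the trigger as "if a participant's status with respect to any of the study criteria change during the experiment". A parenthesis then mentions starting substance abuse. The consequence is that "the participant's participation in the study may be terminated without their consent". The same section says that the consent form will state the circumstances in which termination is anticipated.

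**Timing.** Section 10 (Study Procedures) states: "Randomization will occur at time of consenting". Section 18 repeats this. Telephone follow-up is at 6 months and 1 year (Section 10, Aims 1.2 and 2.2).

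**Criteria.** Patients qualify by "endorsing at least 1 out of 4 cognitive symptoms on the Neurobehavioral Symptom Inventory (NSI") and if they "have been on stable doses of any psychotropic medications for the past 2 months" (Inclusion Criteria). Current or recent substance or alcohol dependence is an exclusion.

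**Withdrawal.** Section 13 lets a participant who wishes to withdraw stop stimulation and remain in data collection. It has no equivalent for someone terminated by the investigator.

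**Analysis.** Section 11 states: "Expected attrition will be taken into account with an intention-to-treat analysis". It adds linear mixed models and a check for informative missingness, with adjustment by an unnamed method. Section 14 repeats this text.

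**MRI.** Section 16 states: "Participants with any MRI scanning contraindications will be excluded from study participation". Section 2 states: "MRI sequences for characterization of TBI may be obtained as part of baseline and post-stimulation assessment in a subgroup of mmTBI subjects". The Exclusion Criteria contain no general MRI item.

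**The concern.** The rule ends participation in the study, not only stimulation, and it reaches any criterion. Two of the criteria can plausibly move with what the trial measures. A participant whose depression persists may have medication started or changed, and depression is the Aim 2 outcome. New substance use may also accompany poor mood or function. If such participants are removed more often from one arm, the 6- and 12-month contrasts compare selected remainders. Central hypothesis 3 and Aims 1.2 and 2.2 rest on those visits. An assessment that the protocol cancelled cannot be recovered at analysis.

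The MRI rule raises a different problem. It removes randomised people from the trial over a procedure that most of the trial does not need, on a ground that the eligibility list does not contain.

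**Working it through.** **1. The plan's own figure.** No figure in the documents measures this concern. The nearest is the power statement in Section 11: 40 versus 40, d = 0.7, 80% power, two-sample t-test. Alpha is not stated; I assume 0.05 two-sided.

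- Noncentrality = 0.7 × √(40/2) = 3.13. Power is 87.1% (t) or 87.9% (normal approximation), so the stated 80% is not reproduced.
- 33 per arm gives 80%, so there is room for 7/40 = 17.5% loss, though the plan states no allowance.
- Loss unrelated to outcome of 0, 10, 20 and 30% in both arms gives power of 87.1, 83.4, 78.7 and 73.0%.

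The mismatch is a separate matter and does not affect this point. Lost precision is tolerable at modest rates; the issue is selective loss.

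**2. Can the rule act selectively on randomised people?**

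| Step | Source | Reading |
|---|---|---|
| Randomised at consent | Sections 10, 18 | Any later change is post-randomisation |
| Any study criterion | Section 14 | Scope is wide; the parenthesis names substance abuse |
| Stable psychotropic doses | Inclusion Criteria | Can change with depression |
| What is ended | Section 14 | Study participation, at discretion |
| Continued data collection | Section 13 | Only for voluntary withdrawal |
| Visits exposed | Section 10 | Mainly 6 and 12 months |
| Primary endpoint | Section 5 | EXAMINER change from before to after stimulation, so less exposed |

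The answer is yes, if the discretion is used.

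**3. Size, on assumed rates.** Let p be the share of an arm removed and g the gap between retained and removed participants, in SD. The full-arm mean is (1 − p) × retained + p × removed, so the retained mean is off by p × g. With the same g in both arms, the bias in a complete-case contrast is (difference in p) × g.

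Example (assumed): 15% of sham and 5% of active removed, removed participants 1 SD worse. The bias is 0.15 × 1 − 0.05 × 1 = 0.10 SD against active.

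| Difference in share removed | g = 0.5 SD | g = 1 SD |
|---|---|---|
| 0 points | 0 | 0 |
| 5 points | 0.025 SD | 0.05 SD |
| 10 points | 0.05 SD | 0.10 SD |
| 20 points | 0.10 SD | 0.20 SD |

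The sign reverses if active loses more of its poor scorers.

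Extreme case: only the worst-scoring share q of sham is lost, and nobody from active. The sham mean then rises by φ(z_q)/(1 − q), which is 0.109, 0.195 and 0.350 for q = 5, 10 and 20%. A true difference of 0.70 becomes 0.591, 0.505 and 0.350. With no true effect, the two-sided 5% test rejects in about 8.6, 14.9 and 35.4% of 20,000 simulated trials.

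All of these are complete-case figures. The planned mixed models would recover part of the bias where earlier recorded scores explain the loss. The 0.7 is an assumption about cognition, not about one-year symptom or mood scores, so it is only a rough yardstick here.

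**4. MRI.** Section 10 places optional MRI after group assignment. Section 16 places the safety form before the scan and makes a contraindication a ground for leaving the study. As written, then, the exclusion can follow randomisation.

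**5. What counts as a change.** The Inclusion Criteria admit people on stable psychotropic doses. Section 16, under tDCS, describes excluding patients on psychotropic medications as a precaution. Until the two are reconciled, a criterion change on medication has no clear meaning.

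**The case against.** The best case for the plan is that the clause is narrow and rarely used. Termination is discretionary. The parenthesis about substance abuse is introduced by i.e. and may be meant to limit the clause. The consent form, which is not in the public document, may narrow it further. Section 13, the dedicated withdrawal section, lists no such termination. This lowers the likely frequency, and it stands. It does not close the gap: nothing in the protocol governs the discretion, and nothing says that follow-up continues once it is exercised.

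Four stronger readings are tempting, and the documents do not support them:

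- **Responders would be terminated when their symptoms resolve.** A reader might infer this because the NSI cognitive items serve both as an entry criterion and as an Aim 1.2 outcome. The reading is strained, since Aim 1.2 exists to follow symptom reduction to one year. Taken that literally, the clause would also remove anyone who turned 56.
- **The rule contradicts intention-to-treat.** No text drops terminated participants or their collected data from the analysis. The plan expects attrition and provides mixed models and a missingness check. The intention-to-treat set is undefined, but that is a gap, not a conflict.
- **Safety follow-up would end after a seizure.** This is not stated. Section 12 requires all adverse events during the study to be collected and reported. Whether that covers terminated participants is left open.
- **The MRI rule makes retention depend on outcome.** A contraindication is normally a pre-existing feature. Implanted electrical devices, artificial craniotomy covers and pregnancy are already in the exclusion list, and prescreening precedes consent, so some cases would be caught before randomisation.

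**Conclusion.** The concern holds in a limited form and should be fixed. Section 14 permits investigator termination of randomised participants from the whole study when a criterion changes, and no text keeps them in follow-up. Used as written, it can make 6- and 12-month retention depend on outcome, most plausibly through medication change or new substance abuse. That undermines the intention-to-treat plan. Aims 1.2 and 2.2 carry most of the exposure.

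The size of any bias is unknown, because the documents give no rates of criterion change or of termination. The 0.10 SD figure is illustrative. It rests on a 10-point difference in removal, a 1 SD gap and a complete-case contrast; with equal removal and equal gaps the bias is zero.

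The MRI rule is a second, independent defect: an unnecessary post-randomisation exclusion, unrelated to outcome.

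**What to change.** 1. **Section 14.** State that a change on an entry criterion after randomisation does not end data collection; that all scheduled assessments (immediate, 1, 6 and 12 months) and adverse-event follow-up continue unless the participant withdraws consent; and that the change and its date are recorded. Whether stimulation continues is a separate clinical decision, not addressed here.
2. **Section 16, MRI.** Limit the exclusion to the MRI procedure, consistent with the optional subgroup use in Sections 2 and 10 and with the Exclusion Criteria.
3. **Psychotropic medication.** Reconcile the Inclusion Criteria with the statement in Section 16, so that it is clear what counts as a criterion change. Which statement is right is for the investigators to settle.

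The cost is a short amendment, matching consent wording and a few more follow-up calls. Participants whose treatment changes stay in the analysis, as intention-to-treat already implies.

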## **15. Data and Specimen Banking (see section on Data Management)**

## **16. Risks to Subjects**

Participation in this study for both healthy controls and mmTBI subjects may involve minor risks and/or discomforts associated with possible breach of confidentiality risk, neuropsychological testing, MRI, EEG, and tDCS.

**MRI:** Radio and magnetic waves associated with MRI scans are not associated with any known adverse effects. MRI is non-invasive and considered minimal risk by the FDA and OHRP. However, the scanner is a large magnet, so it could move objects containing ferrous metal in the room during the scan. All control and mmTBI participants are screened using the MRI safety screening form prior to being scanned. Participants with any MRI scanning contraindications will be excluded from study participation. Participants may be bothered by feelings of

**PROTOCOL TITLE:** Transcranial direct current stimulation for treatment of deficits after traumatic brain injury.

claustrophobia (uncommon). The MRI also makes loud ‘drum’ beating noises during the study. Headphones are provided for protection. Rarely, large or recent tattoos can heat up during an MRI scan and cause skin irritation like a sunburn (uncommon). No long-term harmful effects from MRI are known. However, since the effect of MRI on early development of the fetus is unknown, participants who are pregnant will not be allowed to go in the MRI. Females 18 years of age or older who suspect they may be pregnant will be asked to take a urine pregnancy test before being allowed to participate in the study. The test results will only be shared with participant.

**Neuropsychological tests.** The neuropsychological tasks involved in the protocol entail no foreseeable risk, besides perhaps fatigue or mild to moderate demands on attention and cognition. These are typically very marginally significant risks, mitigated by the fact that if a patient fatigues during testing they are given a rest break or are rescheduled. There is also mild psychological risk inherent in testing participants for cognitive abilities.

One potential risk is breach of confidentiality related to collection of sensitive information. Confidentiality issues are significant since this study collects a variety of sensitive data, in particular with respect to substance use. Because personal information is gathered, there exists the risk of possible invasion of privacy. However, our hard copy data is stored in locked cabinets in locked rooms within a locked, security-patrolled building; and there has never been a breach of confidentiality in our lab. Hence we believe that the likelihood of invasion of privacy is minimal.

**EEG:** There is a very small possibility that participants with sensitive skin (e.g., contact dermatitis) may experience some skin irritation from the EEG gel or metal sensor (uncommon).

**tDCS.** There are several risks associated with tDCS treatment and sham procedures, however, based on our experience with this technology (>500 research subjects run to date), we believe that these risks are minimal. Common expectable side effects during tDCS include skin redness, itching sensation, mild fatigue or drowsiness, nausea, and headache. All patients undergoing stimulation with tDCS will be asked to rate their discomfort with these symptoms every ten minutes, and the treatment will be terminated if discomfort rises above 7 on a 10-point anchored Likert scale, or at any time the patient wishes to stop. All efforts will be made to reduce subject discomfort and avoid the rare occurrence of skin burns, including evidence-based techniques such as using saline-soaked sponges with lower concentrations (~15mM) of solution; offering emollient cream for reddened areas following stimulation; preventing electrodes from drying out during stimulation; disinfecting all treatment sponges regularly; not stimulating over skin with lesions or dermatologic conditions; checking skin impedance before stimulation. When these precautions are followed with conventional tDCS protocols (i.e., 1-2 mA stimulation for up to 30 minutes), using optimized safety protocols, significant adverse effects, such as burns on the skin near electrode affixation or heating of the electrodes affecting nearby scalp surface have not been reported.

Rare mood changes with tDCS have been observed in studies of depressed patients, resulting in several cases of hypomania. Most of these patients were taking concurrent antidepressants. Precautions taken in this study include excluding patients on psychotropic medications, and monitoring mood with visual analog scales during stimulation, and pre/post-treatment depressive symptom questionnaires. There has not been a reported instance of suicidality caused by tDCS.

In healthy controls there have been no reported adverse events of TDCS, other than the physical sensations and skin irritation above. Of critical importance is the safety of tDCS in patients with neurological illnesses that may carry some increased vulnerability to either brain damage or seizures. The experimental threshold at which tDCS causes brain injury was found to be two orders of magnitude above the current densities used in humans, making stimulation at the scalp with

**PROTOCOL TITLE:** Transcranial direct current stimulation for treatment of deficits after traumatic brain injury.

contemporary protocols causing brain damage extremely unlikely. tDCS is widely used in post-stroke patients in protocols that place the stimulating electrodes ipsilateral to the lesion and very often close to perilesional areas, without any increased side effects or adverse consequences. Even more reassuring, tDCS at 1.0-2.0 mA has been performed over damaged left frontal cortex in 37 patients with moderate to severe TBIs, who are at the highest risk of post-traumatic seizures and demonstrate the greatest levels of structural damage, without adverse events, seizures, or decrements in neurologic status. A review of and contact with studies registered in clinicaltrials.gov for tDCS in TBI (Spaulding, NYU, U. Leige) did not discover any occurrence of seizures or adverse events.

Safeguard exclusions that the study will have in place are enumerated above, and will ensure that neurologically unstable patients are screened out of the study, or those who might be at higher risk from cranial electrical stimulation. A Data Safety and Monitoring Board composed of [name] and [name], specialists in neurostimulation and seizures respectively, will be meeting with the PI quarterly to review outcome data to ensure rigorous protection of patients, as described below.

